7.2.2 RECIST Criteria

Disease Control Rate:

The disease control rate is based on the data as per local radiological review following the RECIST V1.0 criteria. The disease control rate is defined as the proportion of patients with CR, PR, or SD.

Objective Response Rate:

The overall tumor response will be based on the data as per local radiological review, following RECIST criteria. The ORR is defined as the proportion of patients with CR or PR.

7.2.3 Handling of Missing and Incomplete Data

Prior Antineoplastic Therapy:

Missing or partial dates of antineoplastic therapy will be imputed in order to determine the duration of treatment with each therapy. If the end date of antineoplastic therapy is missing or partial the latest possible date will be imputed up until the day prior to start of study medication (since antineoplastic therapy use is pre-study). Partial start dates of antineoplastic therapy will be imputed as the earliest possible date. It should be noted that use of antineoplastic therapy during the study would be considered a protocol deviation. Imputed dates will be for the purpose of calculating duration only and the listing should display only the partial date information recorded on the CRF.

Adverse Events (AEs):

In the event of a missing severity for a patient's adverse event, no imputation will be made but this should be raised with Data Management for further discussion since no missing data would be expected for this variable.

Partial start dates for adverse events will be imputed in order to determine if the event is treatment emergent. The imputation of partial start dates of adverse events will follow the following rules:

Adverse Event Start Date Imputation	
Available Data (YYYY-MM-DD)	Imputation Rule
YYYY	If the year part is the same as the year of first dose of study medication, impute with the date of first dose of study medication. Otherwise, impute with the 1st of January of the known year.
YYYY-MM	If the known part is same as the date of first dose of study medication then impute with date of first dose of study medication. Otherwise, impute with the 1st of the known month.
All missing	If the known end date is after date of first dose of study medication then impute with the date of first dose of study medication. Otherwise, impute with the date of informed consent.

Concomitant Medications/Significant Non-Drug Therapies:

Patial start and end dates of medications will be imputed to determine if a medication is concomitant. The imputation of partial start and/or end dates of medcations will follow the following rules:

Medication Start Date		Medication End Date	
Available Data (YYYY-MM-DD)	Imputation Rule	Available Data (YYYY-MM-DD)	Imputation Rule
YYYY	If the year part is the same as the year of first dose of study medication, impute with the date of first dose of study medication. Otherwise, impute with the 1st of January of the known year.	YYYY	Impute as 31'st December of the known year.
YYYY-MM	If the known part is same as the date of first dose of study medication then impute with date of first dose of study medication. Otherwise, impute with the 1st of the known month.	YYYY-MM	Impute as the last day of the known month.
All missing	If the known end date is after date of first dose of study medication then impute with the date of first dose of study medication. Otherwise, impute with the date of informed consent.	All missing	Impute as date of last contact

Disease Progression:

If disease progression or death is documented after one single missing tumor assessment, the actual event date of disease progression/death will be used for the PFS event date. If disease progression is documented after two or more missing tumor assessments, the PFS time of the patient will be censored at the date of the last tumor assessment with overall lesion response of CR, PR or SD.

Additional sensitivity analyses will be performed where:

1. The actual event date of disease progression/death will be used for the PFS event date, irrespective of whether it is preceded by missing tumor assessments;
2. In case of a documented progression/death after one or more missing tumor assessments, disease progression is considered to have occurred at the next scheduled tumor assessment after the date of the last tumor assessment with overall lesion response of CR, PR, or SD.

Duration of Response:

The same rules for missing data for calculation of duration of response will be applied as for PFS described above.

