All study patients must be thoroughly informed about all aspects of the study, including the study visit schedule, required evaluations, and all regulatory requirements for informed consent. The written informed consent must be obtained prior to the performance of any screening evaluations. If the patient is unable to read, an impartial witness should be present during the entire informed consent discussion. The following criteria apply to all patients enrolled into the study, unless otherwise specified.

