7.6.1 Adverse Events

An AE, for the purposes of this protocol, is the appearance of (or worsening of any pre-existing) undesirable sign(s), symptom(s), or medical condition(s) occurring after signing the informed consent, even if the event is not considered to be related to the study drug (study drug refers to the drug under evaluation [RAD001], and study treatment also refers to RAD001).

Adverse events will be assessed according to the CTCAE, version 3.0. If CTCAE grading does not exist for a particular AE, the severity of mild, moderate, severe, and life-threatening, or grades 1 to 4, will be used. The CTCAE grade 5 (death) will not be used in this study; rather, this information will be collected on the End of Treatment or Survival Information CRF page. All AEs will be coded by System Organ Class (SOC) and preferred term using the Medical Dictionary for Regulatory Activities (MedDRA), latest version.

Adverse event monitoring should be continued for at least 4 weeks following the last dose of study treatment. Adverse events (but not SAEs) occurring before starting study treatment, but after signing the informed consent form, are recorded on the Medical History/Current Medical Conditions CRF pages. Abnormal laboratory values or test results constitute an AE only if they induce clinical signs or symptoms, are considered clinically significant, or require therapy (e.g., any hematological abnormality that requires transfusion or cytokine treatment); and should be recorded on the Adverse Events CRF page under the signs, symptoms, or diagnosis associated with them. In addition, isolated abnormal laboratory values that are considered clinically significant (e.g., cause study discontinuation or constitutes in and of itself a SAE) should be recorded on the Adverse Events CRF page. Serious AEs occurring after signing the Informed Consent are recorded on the Adverse Event CRF page.

The occurrence of AEs should be sought by non-directive questioning of the patient at each visit during the study. Adverse events may also be detected when they are volunteered by the patient during or between visits or through physical examination, laboratory test, or other assessments.

As far as possible, each AE should be evaluated to determine:

1. The severity grade (CTCAE grades 1 to 4);
2. Its relationship to study drug (suspected/not suspected);
3. Its duration (start and end dates or if continuing at final exam);

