8.1 Adverse Events

All AEs will be coded using the Medical Dictionary for Regulatory Activities (MedDRA®) Version 12.1 to provide the system organ class (SOC) and preferred term for each AE.

An adverse event will be defined as treatment emergent if it begins on or after the first day of dosing with study medication and no later than 30 days after the last dose of study medication. It is expected that adverse event monitoring will continue for at least 4 weeks after the last dose of study medication but new events occurring after the end of the treatment period will not be recorded on the CRF (unless they are serious or lead to death).

Since adverse events occurring prior to start of study or between signing informed consent and start of study medication should be considered as medical history, it is anticipated that all adverse events will be treatment emergent adverse events. However, in the event of any non-treatment emergent adverse events occurring, these will be indicated on the adverse event listings. Non-treatment emergent adverse events are defined as events that begin prior to the first day of dosing. If these events are Serious Adverse Events (SAEs) then they will also be summarized.

The number of patients experiencing each of the following will be summarized:

- At least one treatment emergent adverse event (TEAE)
- At least one SAE
- At least one SAE with a suspected relationship to study medication
- At least one adverse TEAE event leading to death
- At least one TEAE leading to modification of study medication
- At least one TEAE leading to permanent discontinuation of study medication
- At least one severe TEAE
- At least one TEAE with a suspected relationship to study medication

Serious adverse events will be indicated on the CRF, as will adverse events leading to modification or permanent discontinuation of study medication. The addition of non-drug therapy will not be classed as a modification of study medication.

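### An adverse event with no start date and no known end date is placed at consent, and so drops out of the treatment-emergent counts

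*SAP*

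**What the plan says.** The SAP 7.2.3 table for AE start dates has a stated purpose: "Partial start dates for adverse events will be imputed in order to determine if the event is treatment emergent". If only the year, or the year and month, is known and it matches first dose, the start is set to first dose. If nothing is known, the row has two branches: "If the known end date is after date of first dose of study medication then impute with the date of first dose" and, for all other cases, "Otherwise, impute with the date of informed consent".

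SAP 8.1 counts an event as treatment-emergent if it "begins on or after the first day of dosing with study medication" and no later than 30 days after the last dose. Conversely, "Non-treatment emergent adverse events are defined as events that begin prior to the first day of dosing". Those events are marked in the listings and are summarized only if serious.

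Protocol 7.6.1 says where events before treatment are kept. Non-serious events arising between consent and first dose "are recorded on the Medical History/Current Medical Conditions CRF pages"; serious events go on the AE page from consent onwards. On that basis SAP 8.1 says "it is anticipated that all adverse events will be treatment emergent adverse events".

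On the order of consent and dosing, Protocol Section 5 says: "The written informed consent must be obtained prior to the performance of any screening evaluations".

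**The concern.** The branch that assigns first dose depends on a known end date. An event with no end date cannot meet that condition, so it falls to the consent date and is classed as starting before treatment. Protocol 7.6.1 allows an event to be recorded as continuing at the final examination instead of with an end date, so the case is foreseeable. An undated event still unresolved at the end of the study would then be treated as pre-treatment, while one that resolved the day after first dose would count as treatment-emergent.

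Describing the safety profile is a stated objective, and the treatment-emergent table by system organ class and preferred term is its main display. There is no control arm in which the same undercount would also appear. An error in one direction therefore lowers the reported incidence directly.

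**Working it through.** The plan states no figure for this point, so there is nothing to reproduce. The check applies the rule to each possible end date and then gives the size per patient.

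**Inputs.** The start-date rule is in SAP 7.2.3 and the treatment-emergent definition in SAP 8.1. Protocol Section 5 puts consent before any screening evaluation, hence before first dose. The planned size is 110 in Protocol Section 4 and 142 in SAP Section 3. Consent was set, as an assumption, at 1, 7, 28 and 35 days before first dose.

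**Rule as written, start date wholly missing.** Start = first dose if a known end date is after first dose; otherwise start = consent. The event is treatment-emergent if its start lies between first dose and 30 days after last dose. The alternative is: start = consent if a known end date is before first dose; otherwise start = first dose.

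| End date | Start under SAP | Treatment-emergent under SAP | Treatment-emergent under alternative |
|---|---|---|---|
| Missing or ongoing | Consent (day -1 to -35) | No | Yes |
| Before first dose | Consent | No | No |
| On first-dose day | Consent | No | Yes |
| After first dose | First dose | Yes | Yes |

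The result is the same at all four consent intervals. The alternative changes two rows, both by adding treatment-emergent events. It still leaves out events known to have ended before dosing.

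**Against the SAP's other rows.** With a year, or a year and month, that matches first dose, the SAP assumes an on-treatment start. Only the row with the least information defaults to a pre-treatment start.

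**Whether another section repairs it.** SAP 8.1 refers the reader to 7.2.2 for missing AE start and end dates. Section 7.2.2 defines disease control and response under RECIST. The missing-data rules are in 7.2.3, which imputes no AE end date.

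**Size.** Loss in an incidence = k/N, where k is the number of patients whose only qualifying event is affected.

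- k = 1: 1/110 = 0.9 points; 1/142 = 0.7 points.
- k = 10: 10/110 = 9.1 points; 10/142 = 7.0 points.

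The documents do not give k, so 1 to 10 is an assumed range for scale only. The actual denominator is the Safety population, whose size is not known at planning.

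**The case against.** Several arguments limit the point, and most of them stand.

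- **Few events qualify.** Protocol 9.4 sends omissions back to sites as queries, and 9.1 requires full verification of the data for safety variables. Only an event without even a start year after that process reaches this row. This stands, and it is why the point is minor.
- **Ongoing may not mean missing.** The AE listing shell shows ongoing as its own entry in the end-date column. A programmer could reasonably read it as extending past first dose. That is possible, but the SAP does not say so, and on the literal text an ongoing event has no known end date.
- **The AE page is not strictly post-dose.** Table 9 of the protocol marks the AE row at screening and baseline, its footnote sends all events after the start of the study to the AE page, and SAP 8.1 provides for non-treatment-emergent events. The recording rule therefore makes an on-treatment start likely for a non-serious event; it does not prove it.

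A reader might also infer four stronger conclusions that the documents do not support.

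- *Every affected event is misclassified.* Serious events between consent and first dose belong on the AE page, so an undated one may correctly be non-emergent.
- *Events disappear from the report.* Non-emergent serious events are still summarized, fatal or life-threatening events are serious by definition in Protocol 7.6.1, and SAP 8.1 lists all events regardless of emergence.
- *Events certainly drop out of the death, discontinuation and modification rows.* The SAP 8.1 text limits those rows to treatment-emergent events, but the shell for Table 14.5-1.1 labels them simply as adverse events. The effect depends on which label is programmed.
- *The medication rule has the same fault.* Its start-date wording is the same, but a wholly missing medication end date is set to last contact, and SAP 7.5 counts as concomitant anything ending after the start of study medication. With both dates missing, or with an end after first dose, the classification is the same whichever start is imputed.

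**Conclusion.** The point holds for AEs with no start date and no known end date. The rule as written makes them non-treatment-emergent, against the SAP's expectation for events on the AE page and against its partial-date rows. For these events the error runs one way, towards fewer treatment-emergent events.

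The conclusion rests on a literal reading of the row, on consent at least a day before first dose, and on sites recording non-serious pre-treatment events as medical history. The loss is about 0.9 points (N = 110) or 0.7 points (N = 142) per patient whose only qualifying event is affected, and the number of such patients is unknown and probably small. No efficacy result or decision rule depends on it. It is worth correcting because the rule gives the less likely answer and the correction is nearly free.

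**What to change.** In SAP 7.2.3, replace the AE row for a wholly missing start date with: impute the date of first dose unless a known end date is before first dose, in which case impute the date of informed consent; an event whose end date is missing or recorded as ongoing takes the first-dose date.

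In SAP 8.1, correct the cross-reference for missing AE dates from 7.2.2 to 7.2.3. Leave the medication start-date rule as it is, since a change there would not alter concomitant classification in practice.

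The cost is one sentence, one section number and a small change to the derivation program. No new data or CRF change is needed.

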6.6.4 Concomitant Medications

Patients will be instructed not to take any additional medications (including over-the-counter products) during the course of the study without prior consultation with the investigator.

At each visit, the investigator will ask the patient about any new medications he/she is or has taken after the start of the study drug. All medications taken ≤ 30 days prior to study entry should be recorded on the Concomitant Medications/Significant Non-Drug Therapies Prior to Start of Study Drug CRF page. All medications (other than the study drug) and significant non-drug therapies (including physical therapy and blood transfusions) administered after the patient starts treatment with study drug must be listed on the Concomitant Medications/Significant Non-Drug Therapies CRF. Prior and concomitant medications will be coded to indication-specific Anatomic Therapeutic Chemical classification (ATC) and preferred name using the World Health Organization (WHO) Drug Dictionary (latest version).

Permitted treatments during the study include:

- Bisphosphonate therapy for treatment of bone metastases. This therapy should be initiated before the patient is enrolled into the study;
- Pain medication to allow the patient to be as comfortable as possible;
- Localized radiotherapy, for the treatment of pre-existing, painful bone metastases is allowed during the study only if evidence of radiological progression is not present. Radiotherapy for brain metastases is not permitted during the course of the study (the need for CNS radiation will constitute disease progression);

- Nutritional support as recommended by the investigator;
- Megesterol acetate may be prescribed during the course of the study as an appetite stimulant;
- Oxygen therapy and blood transfusions.

The following restrictions apply during the entire duration of the study:

- No other investigational therapy should be given to patients;
- No anticancer agents other than the study drug (RAD001) should be given to patients. If such agents are required for a patient, then the patient must first be withdrawn from the study;
- Leukocyte growth factors (e.g., colony-stimulating factor and granulocyte-macrophage colony-stimulating factor) are not to be administered prophylactically, but may be prescribed by the investigator for severe neutropenia if this is thought to be appropriate;

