A chest x-ray will be performed at Screening Visit 1a. These data will be summarized presenting the investigator's assessment of abnormality for the safety population.

Data for all chest x-ray assessments throughout the study (including unscheduled) will be listed.

Medications (other than study medication) and significant non-drug therapies used throughout the treatment period are captured on the CRF. These will be coded using the Novartis Drug and Therapy Dictionary (Version Sep 2009). Those that start on or after the first day of dosing with study medication and no later than 30 days after the last dose of study medication, and those that end after the start of study medication (even if started prior to study medication) will be defined as concomitant and will be summarized. Summaries will be presented by Anatomical Therapeutic Classification (ATC) class and preferred term for the safety population. If a patient takes multiple medications/therapies within an ATC class or within an ATC class and preferred term, the patient will be counted once.

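### SAP 7.2.3 imputes partial start dates to the first dose without checking the end date, so some short courses stopped before dosing count as concomitant; the 30-day limit in SAP 7.5 excludes nothing

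*SAP*

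**What the plan says.** SAP 7.2.3 gives the purpose of the medication rules: partial "start and end dates of medications will be imputed to determine if a medication is concomitant". The start-date rows are:

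- Year only: if it is the "same as the year of first dose of study medication, impute with the date of first dose of study medication"; otherwise 1 January of that year.
- Year and month: "If the known part is same as the date of first dose of study medication then impute with date of first dose"; otherwise the first of that month.
- Completely missing: "If the known end date is after date of first dose of study medication", the first-dose date is used; otherwise the consent date. This is the only start row that refers to the end date.

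Partial medication end dates go to the last day of the known month or year. For a fully missing end date the rule is "Impute as date of last contact".

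The adverse event table in the same section has the same start rows; for a matching month the instruction is again "then impute with date of first dose of study medication". It has no rule for imputing end dates.

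SAP 7.5 then has two alternative clauses for concomitant use. The first covers drugs starting between first dose and 30 days after last dose, with no condition on the end. The second covers "those that end after the start of study medication (even if started prior to study medication) will be defined as concomitant", with no condition on the start.

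Protocol 10.3.2 counts a drug begun before treatment only if it continues once treatment has started. Protocol 6.6.4 collects earlier drugs on purpose: those taken up to 30 "days prior to study entry should be recorded on the Concomitant Medications/Significant Non-Drug Therapies Prior to Start of Study Drug CRF page".

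**The concern.** Where the year or month matches, the rule replaces an uncertain start with the first-dose date even if the recorded end date shows that the drug had already stopped. The imputed start then satisfies the first clause of SAP 7.5 by itself. The record ends up with its start after its end and appears in the concomitant table, although Protocol 10.3.2 would leave it out.

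The adverse event rows have the same gap. Serious events after consent but before dosing go on the Adverse Event page (Protocol 7.6.1), so such a record can exist and would be labelled treatment-emergent.

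The second clause of SAP 7.5 raises a separate question of logic: whether the 30-day limit in the first clause can ever exclude a drug. At stake is the accuracy of descriptive safety tables and flags.

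**Working it through.** The documents give no figure on this point, so there is none to reproduce. The check applies the SAP 7.2.3 rows and the SAP 7.5 clauses, as written, to assumed dates: consent 20 Feb 2010, first dose 20 Mar 2010, last dose 20 Sep 2010, last contact 1 Mar 2011.

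Clause 1: start from 20 Mar 2010 to 20 Oct 2010 (20 Sep + 30 days). Clause 2: end after 20 Mar 2010. A drug is concomitant if either holds.

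| Recorded start | Recorded end | Start used | End used | Clause 1 | Clause 2 | Concomitant |
|---|---|---|---|---|---|---|
| 2010 | 5 Mar 2010 | 20 Mar 2010 | 5 Mar 2010 | yes | no | yes, wrongly |
| 2010-03 | 10 Mar 2010 | 20 Mar 2010 | 10 Mar 2010 | yes | no | yes, wrongly |
| 2010 | 2010-02 | 20 Mar 2010 | 28 Feb 2010 | yes | no | yes, wrongly |
| 5 Jan 2010 | 5 Mar 2010 | 5 Jan 2010 | 5 Mar 2010 | no | no | no |
| missing | 5 Mar 2010 | 20 Feb 2010 | 5 Mar 2010 | no | no | no |
| 2009 | 5 Mar 2010 | 1 Jan 2009 | 5 Mar 2010 | no | no | no |
| 2010-02 | 28 Feb 2010 | 1 Feb 2010 | 28 Feb 2010 | no | no | no |
| 2010 | 10 Apr 2010 | 20 Mar 2010 | 10 Apr 2010 | yes | yes | yes, correctly |
| 19 Nov 2010 | 10 Dec 2010 | 19 Nov 2010 | 10 Dec 2010 | no | yes | yes |
| 17 Feb 2011 | missing | 17 Feb 2011 | 1 Mar 2011 | no | yes | yes |

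**Partial starts (rows 1 to 8).** In the first three rows the imputed start falls 15, 10 and 20 days after the drug's own end. Those ends are within 30 days of first dose, so Protocol 6.6.4 would collect the drugs even if study entry is taken as the first dose. The next four rows show that a full date, a fully missing start, an earlier year or a non-matching month gives the right class. Knowing only the matching year therefore gives a worse answer than knowing nothing. Row 8 shows that a drug still in use at first dose is concomitant in any case. Misclassification needs both conditions: a partial start that matches the first-dose year or month, and an end before first dose.

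**Upper limit (rows 9 and 10).** These drugs start 60 and 150 days after last dose. In general:

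- if start > last dose + 30 days, then start > first dose;
- end ≥ start, so end > first dose and clause 2 holds.

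The limit therefore cannot exclude any drug. Enumeration agrees: starts 31 to 799 days after last dose (769 values) with durations 0 to 59 days (60 values) give 769 × 60 = 46,140 combinations, and none was excluded.

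**Adverse events.** A serious event with start 2010-03 and end 10 Mar 2010 gets a start of 20 Mar 2010. SAP 8.1 defines treatment-emergent as beginning from the first day of dosing to 30 days after last dose, so the event qualifies. It would enter Table 14.5-2.1 and the treatment-emergent line of Table 14.5-1.1.

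**The case against.** The strongest defence is that the documents show the intent and offer other ways to sort these records. Protocol 10.3.2 is clear. Drugs taken before treatment go on a separate case report form page, and Listing 16.4-1.1 carries a prior-medication flag. SAP 7.5 also introduces its definition by speaking of drugs used during the treatment period, so a drug stopped earlier is arguably outside its scope. This makes the error less likely in practice but does not remove it: the SAP presents the date rules as the means of deciding concomitant status and does not refer to the separate page.

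Imputing towards the first dose can also be defended as conservative. That holds where the dates leave doubt. Here the recorded end date settles the question.

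The objections to reach are sound. A reader might infer that long-standing drugs are the main group affected, because their start dates are often vague. The documents do not support that: a start in an earlier year is imputed to 1 January of that year and classified correctly. Nor is every year-only start in the first-dose year at risk, because a drug still in use at first dose is concomitant whatever its start.

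A reader might also infer that the concomitant table would fill with post-treatment drugs. SAP 7.5 describes capture during the treatment period. Protocol 6.6.6.1 sets the follow-up visit 28 days after last dose, inside the limit. Protocol Section 4 counts the 28 days from the End-of-Treatment Visit, which with the two-week allowance in 6.6.6.1 could reach day 42 (28 + 14), so late records are possible but should be few. Later anticancer therapy has its own listing (16.4-2.1).

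On adverse events, non-serious pre-dose events go to medical history, and SAP 8.1 summarises pre-dose serious events anyway. Mainly the treatment-emergent label changes.

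**Conclusion.** The point holds and is minor. As written, SAP 7.2.3 and 7.5 together misclassify any medication whose partial start matches the first-dose year or month and whose end, known or imputed from a partial date, is before first dose. The result contradicts Protocol 10.3.2. The 30-day limit in SAP 7.5 has no effect as worded, though few records are likely to test it.

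The effect is limited to Table 14.4-1.1, the prior-medication flag in Listing 16.4-1.1, and a few treatment-emergent flags with the tables that use them. PFS, OS and response do not depend on these rules. How many records are affected cannot be derived from the documents; it depends on how often a short course stopped before dosing was entered with a partial start.

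The conclusion rests on a literal reading of the two clauses in SAP 7.5 as alternatives. The sponsor may have meant the second only for drugs begun before treatment, but its parenthesis extends the clause to early starts and does not confine it to them.

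**What to change.** In SAP 7.2.3, add a condition to the year and year-month start rows for both medications and adverse events: use the first-dose date unless the end date (known, or for medications as imputed from a partial date) is before the first dose, in which case impute the earliest possible date. Including imputed medication end dates is needed to correct the third row of the table above.

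In SAP 7.5, define a concomitant drug as one with a start no later than 30 days after last dose AND either a start on or after first dose, or an end after first dose or still ongoing. This keeps the present requirement that the end be after first dose and does not extend it to the first-dose day.

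On the worked examples, the three wrongly included drugs get starts of 1 Jan, 1 Mar and 1 Jan 2010 and drop out. The two drugs started 60 and 150 days after last dose also drop out, and the other five rows keep their class. One boundary case remains: a partial-start record ending on the first-dose day would still count, with start and end on the same day.

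The cost is a few lines of SAP text, a small change to the date-derivation code and its quality control. Design, data collection and efficacy analyses are unchanged.
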